3.3.2 Dose Delays and Discontinuation of CUDC-907

In the event that any of the above criteria are not met, study drug dosing will be held until the retreatment criteria are met. Treatment may then resume at the full dose of CUDC-907, as long as none of the criteria in **Table 4** and/or **Table 5** are met. Beyond Cycle 1, subjects held for > 7 days may restart treatment after the subject has met the above criteria at the discretion of the Investigator. Beyond Cycle 2, subjects may have study drug held for up for 1 full cycle (21 days). If beyond 1 full cycle, then the subject will be taken off treatment per section **4.9.2**.

Subjects who experience a DLT-like event will be either discontinued from further study treatment or their dose will be reduced as outlined in **Table 3**. A DLT-like event will be defined as any of the following AEs occurring at any time:

- Non-hematological \geq Grade 3 AE, other than Grade 3 nausea or Grade 3 vomiting in subjects treated with less than optimal antiemetic therapy.
- An AE resulting in a dose delay of 21 days.
- Grade 4 neutropenia \geq 7 days, or \geq Grade 3 neutropenia with fever > 101.3°F (38.5°C) or \geq Grade 3 neutropenia with infection.
- Grade 4 thrombocytopenia \geq 7 days, or \geq Grade 3 thrombocytopenia and significant bleeding.

Table 3 CUDC-907 Dose Reduction Steps

Reduction Steps:	Schedule	Dose
Starting dose	5/2	60 mg
Dose Reductions	Schedule	Dose
First dose reduction	4/3	60 mg
Second dose reduction	5/2	30 mg
Final dose reduction	4/3	30 mg

4/3 = 4 days on, 3 days off; 5/2 = 5 days on, 2 days off

Dose Adjustments for CUDC-907 Hematologic and Non-hematologic Toxicity

The administration of HDAC and PI3K inhibitors has been associated with predictable bone marrow suppression that is typically transient and reversible.

The administration of HDAC and PI3K inhibitors has also been associated with hyperglycemia. This hyperglycemia does not generally result in severe metabolic complications and typically resolves with therapeutic intervention. The treatment goal for glycemic control is fasting plasma glucose < 160 mg/dL; while making every attempt to avoid hypoglycemia. Dose modifications of CUDC-907 are based on the severity of toxicities.

CUDC-907 dose adjustments for hematologic and non-hematologic toxicities are shown in **Table 4** and **Table 5**.

Table 4 CUDC-907 Dose Adjustments for Hematologic and Non-Hematologic Toxicities			
Thrombocytopenia	Grade 1 or 2 No change in dose	Grade 3 or 4 (platelets < 50,000/μL) Hold treatment until platelets \geq 50,000/ μ L or baseline, then reduce dose to the next lower dose level (as applicable per Table 3).	Grade 4 thrombocytopenia requiring platelet transfusion Hold treatment until platelets \geq 75,000/ μ L or baseline, then reduce dose to the next lower dose level (as applicable per Table 3).
Neutropenia	Grade 1 or 2 No change in dose	Grade 3 or 4 (ANC < 1,000/μL) Hold treatment until ANC \geq 1000/ μ L, then reduce dose to the next lower dose level (as applicable per Table 3).	Grade 4 febrile (\geq 38.5° C) neutropenia Hold treatment until febrile neutropenia resolves and ANC \geq 1000/ μ L or baseline, then permanently dose reduce to the next lower dose level (as applicable per Table 3).
Anemia	Grade 1 or 2 No change in dose	Grade 3 or 4 (hemoglobin < 8 g/dL) Hold treatment until hemoglobin \geq 10 g/dL or baseline then reduce dose to the next lower dose level (as applicable per Table 3).	Grade 4 anemia requiring transfusion Hold treatment until hemoglobin \geq 10 g/dL or baseline, then permanently dose reduce to the next lower dose level (as applicable per Table 3).

Recurrence of Grade 3 or 4 hematologic toxicity will be cause for a second dose modification.
 
If the starting dose does not permit dose modification, then study drug will be discontinued.
			

Table 4			
CUDC-907 Dose Adjustments for Hematologic and Non-Hematologic Toxicities			
Non-hematological AEs (excluding hyperglycemia)	Grade 1 or 2 No change in dose ¹	Grade 3 
 • Hold treatment until resolution to ≤ Grade 1 or baseline • If not recovered to ≤ Grade 1 or baseline within 3 weeks, reduce to next lower dose level upon return to ≤ Grade 1 or baseline (as applicable per Table 3). 	Grade 4 Discontinue treatment. ²
Recurrence of Grade 3 non-hematologic toxicity (excluding hyperglycemia) or inability to reduce dose (based on starting dose) will be grounds for discontinuation of study drug.			

Table 5 CUDC-907 Dose Adjustments for Hyperglycemia			
Toxicity	Management		
Hyperglycemia	Grade 1/2 or Grade 3 (> 250 – 500 mg/dL) asymptomatic; No change in dose ¹	Grade 3 (> 250 – 500 mg/dL) symptomatic or Grade 4 (> 500 mg/dL) Hold treatment until glucose < 250 mg/dL and asymptomatic; Reduce dose to the next lower dose level (as applicable per Table 3).	≥ Grade 3 hyperglycemia not improving despite appropriate treatment for 1 week or symptomatic Grade 4 hyperglycemia (> 500 mg/dL) Hold treatment until glucose < 250 mg/dL and asymptomatic; Reduce dose to the next lower dose level (as applicable per Table 3) upon return to ≤ Grade 1 or baseline.

Recurrence of Grade 3 or 4 hyperglycemia will be cause for a second dose modification. If the starting dose does not permit dose modification, then study drug will be discontinued.
 
Recurrence of Grade 3 or 4 hyperglycemia that does not recover to ≤ Grade 1 or baseline within 3 weeks after second modification (as applicable) will be grounds for discontinuation of study drug.
			

¹ Transient Grade 1 or 2 hyperglycemia will be monitored per Investigator discretion and medical guidelines.

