2 ELIGIBILITY ASSESSMENT AND ENROLLMENT

2.1 ELIGIBILITY CRITERIA

2.1.1 Inclusion Criteria:

- 2.1.1.1 Subjects \geq 18 years of age.
- 2.1.1.2 Thyroid cancer histology or cytology that is aggressive (anaplastic/undifferentiated thyroid cancer, poorly differentiated thyroid cancer, hürthle cell carcinoma, tall-cell variant of papillary thyroid cancer, sclerosing variant of papillary thyroid cancer).
- 2.1.1.3 Measurable disease.
- 2.1.1.4 Eastern Cooperative Oncology Group (ECOG) performance status of 0 to 2.
- 2.1.1.5 Absolute neutrophil count \geq 1,000/ μ L
- 2.1.1.6 Platelets \geq 75,000/ μ L
- 2.1.1.7 Creatinine \leq 1.5x upper limit of normal (ULN) or creatinine clearance \geq 60ml for

- patients with creatinine levels 1.5 times above institutional ULN (calculated based on age, weight and sex)
- 2.1.1.8 Total bilirubin $\leq 1.5x$ ULN; AST/ALT $\leq 2.5x$ ULN. For subjects with documented liver metastases, the AST/ALT may be $\leq 5x$ ULN.
 - 2.1.1.9 Recovery to Grade 1 or baseline of any toxicity due to prior anticancer therapies (excluding alopecia).
 - 2.1.1.10 Platelet transfusions to help patients meet eligibility criteria are not allowed within 3 days prior to screening CBC or Cycle 1, Day 1 treatment.
 - 2.1.1.11 Women of child bearing potential must have a negative serum pregnancy test.
 - 2.1.1.12 The effects of CUDC-907 on the developing human fetus are unknown. For this reason, women of child-bearing potential and men must agree to use adequate contraception (hormonal or barrier method of birth control; abstinence) prior to study entry, for the duration of study participation and for 30 days following the last study treatment. Should a woman become pregnant or suspect she is pregnant while she or her partner is participating in this study, she should inform her treating physician immediately.
 - 2.1.1.13 Able to provide written informed consent and to follow protocol requirements.
- 2.1.2 Exclusion Criteria:
- 2.1.2.1 Systemic anticancer therapy within 4 weeks of study entry, except for subjects with anaplastic/undifferentiated thyroid cancer who may be enrolled immediately after discontinuation of previous therapy.
 - 2.1.2.2 Other investigational agents within 4 weeks prior to study treatment, except for subjects with anaplastic/undifferentiated thyroid cancer who may be enrolled immediately of discontinuation of previous therapy.

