3.3 DOSE MODIFICATION

3.3.1 Subjects may continue to receive 21-day cycles of study treatment until disease progression has been documented or other discontinuation criteria have been met.

To continue dosing of CUDC-907, subjects must meet the following criteria:

- ANC > 1,000/ μ L.
- Platelets \geq 50,000/ μ L.
- AST and ALT \leq 2.5 \times ULN (for subjects with documented liver metastases AST and ALT must be \leq 5 X ULN).
- Total Bilirubin concentration \leq 1.5 \times ULN.
- Creatinine \leq 1.5 \times ULN.
- \leq Grade 2 diarrhea controlled by antidiarrheal treatment.

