7 SAFETY REPORTING REQUIREMENTS/DATA AND SAFETY MONITORING PLAN

7.1 DEFINITIONS

7.1.1 Adverse Event

An adverse event is defined as any reaction, side effect, or untoward event that occurs during the course of the clinical trial associated with the use of a drug in humans, whether or not the event is considered related to the treatment or clinically significant. For this study, AEs will include events reported by the patient, as well as clinically significant abnormal findings on physical examination or laboratory evaluation. A new illness, symptom, sign or clinically significant laboratory abnormality or worsening of a pre-existing condition or abnormality is considered an AE. All AEs must be recorded on the AE case report form unless otherwise noted above in Section 6.2.

All AEs, including clinically significant abnormal findings on laboratory evaluations, regardless of severity, will be followed until return to baseline or stabilization of event. Serious adverse events that occur more than 30 days after the last administration of investigational agent/intervention and have an attribution of at least possibly related to the agent/intervention should be recorded and reported as per sections **7.3, 7.4**.

An abnormal laboratory value will be considered an AE if the laboratory abnormality is characterized by any of the following:

- Results in discontinuation from the study
- Is associated with clinical signs or symptoms
- Requires treatment or any other therapeutic intervention
- Is associated with death or another serious adverse event, including hospitalization.
- Is judged by the Investigator to be of significant clinical impact
- If any abnormal laboratory result is considered clinically significant, the investigator will provide details about the action taken with respect to the test drug and about the patient's outcome.

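### Patients enrolled on creatinine clearance must have drug held at an unchanged baseline, because the continuation criteria omit that route; a lesser wording conflict affects a first asymptomatic Grade 3 hyperglycaemia

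*Combined protocol and SAP*

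**What the plan says.** **Entry.** Protocol section 2.1.1.7 requires creatinine at or below "1.5x upper limit of normal (ULN) or creatinine clearance" of at least 60 ml (no time unit is printed). The clearance route is meant for patients whose creatinine exceeds the limit, with clearance worked out from age, weight and sex.

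**Continuation.** Section 3.3.1 states "To continue dosing of CUDC-907, subjects must meet the following criteria". The only renal item on its list is creatinine no higher than 1.5x ULN. Section 3.6.1, which applies before each cycle, repeats that limit. Neither list offers clearance or a return to baseline as an alternative. When any item fails, section 3.3.2 holds the drug until the criteria are satisfied. The investigator's discretion to restart after a hold of more than 7 days operates only once they are satisfied.

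**Hyperglycaemia.** Section 3.3.2 states "Subjects who experience a DLT-like event will be either discontinued from further study treatment or their dose will be reduced as outlined in" (the reference is to the reduction steps of Table 3). Any non-haematological adverse event of Grade 3 or higher is DLT-like, "other than Grade 3 nausea or Grade 3 vomiting in subjects treated with less than optimal antiemetic therapy". For asymptomatic Grade 3 hyperglycaemia (above 250 and up to 500 mg/dL), Table 5 says "asymptomatic; No change in dose". Its third column moves to a hold and a reduction for "Grade 3 hyperglycemia not improving despite appropriate treatment for 1 week", and a recurrence brings a further dose modification.

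**The concern.** The main worry is that the entry rule and the continuation rule use different tests for the same organ function. A patient can be eligible on clearance, start treatment, show exactly the same creatinine at the next check, and have drug withheld for it. Nothing about that patient's safety has changed. The patient loses planned treatment, and if re-imaged at the planned 6 weeks still counts as evaluable for response, because section 6.4.1 asks only for one cycle of therapy and a re-evaluation. Exposure among evaluable patients then varies for a reason unrelated to toxicity.

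The lesser worry is that two parts of section 3.3.2 give different doses for the same laboratory finding, so that two investigators acting in good faith could dose the same patient differently.

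**Working it through.** The plan gives no figure on this point to reproduce, so the check sets the rules side by side and works out the dose that follows.

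**1. Creatinine rules**

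| Section | Applies to | Creatinine up to 1.5x ULN | Clearance alternative |
|---|---|---|---|
| 2.1.1.7 | Entry | Yes | Yes, at least 60 ml |
| 3.3.1 | Continuing to dose | Yes | None |
| 3.6.1 | Before each cycle | Yes | None |

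The liver-enzyme item is handled differently. The 5x ULN allowance for liver metastases at entry (2.1.1.8) is carried into both 3.3.1 and 3.6.1. The renal allowance is carried into neither, which points to an omission and not to a deliberate tightening.

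Section 3.3.1 speaks of continuing, and 3.6 is headed as criteria for continued treatment, so on the natural reading such a patient can start Cycle 1. At an unchanged creatinine the check before Cycle 2 fails and drug is held. If the phrase about each cycle in 3.6.1 is taken to include the first, Cycle 1 fails too.

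**2. Dose consequence for creatinine** (60 mg, 5 days on and 2 off, three weeks per cycle; restaging after two cycles, section 3.7)

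- Planned per cycle: 60 × 5 × 3 = 900 mg. Planned by first restaging: 2 × 900 = 1,800 mg.
- Held from Cycle 2: 900 / 1,800 = 50%.
- Held from Cycle 1: 0 / 1,800 = 0%.

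**3. Who could enter by the clearance route.** The protocol names no formula and no ULN. Assume Cockcroft-Gault for a man with creatinine 1.6x ULN and a target of 60 ml/min. Weight needed = 60 × 72 × SCr / (140 − age).

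- ULN 1.0 mg/dL (SCr 1.6): age 40, 6,912 / 100 = 69.1 kg; age 60, 6,912 / 80 = 86.4 kg.
- ULN 1.3 mg/dL (SCr 2.08): age 40, 8,985.6 / 100 = 89.9 kg; age 60, 8,985.6 / 80 = 112.3 kg.

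So the route is open, but mainly to heavier or younger patients. This says nothing about how many will enrol.

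**4. When the hyperglycaemia rules collide**

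- The value must be an adverse event. Under section 7.1.1 a laboratory abnormality qualifies if, among other conditions, it "Requires treatment or any other therapeutic intervention". Section 3.3.2 implies treatment at this level: "The treatment goal for glycemic control is fasting plasma glucose" below 160 mg/dL, and Table 5 presupposes a week of treatment.
- It must be asymptomatic. Table 5 itself holds and reduces for symptomatic Grade 3.
- It must be a first episode that improves within a week. Otherwise Table 5 also modifies the dose.

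Inside that window, starting from full dose, the next full cycle is 900 mg under Table 5. Under the DLT-like rule it is 60 × 4 × 3 = 720 mg, which is (900 − 720) / 900 = 20% lower, or 0 mg if treatment is discontinued.

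**5. How often.** Table 2 shows Grade 3 hyperglycaemia in 1 of 44 phase 1 patients (2.3%), pooled over schedules, with symptom status not given. There is no rate for the 5/2 schedule.

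**6. Why the fix should not touch the DLT-like definition.** Section 8 stops enrolment if, after 6 or more patients, DLTs reach one third. It does not define DLT, and the nearest definition is the DLT-like event of 3.3.2. If that definition is the one used, removing an event from it also loosens the stopping rule. For scale, assume independent patients and a check after each one from the sixth to the fortieth. The chance of ever meeting the rule is 0.13 at a DLT rate of 10%, 0.19 at 12.3% and 0.34 at 17%. These rates are assumptions chosen to show sensitivity.

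**7. Efficacy design.** The two-stage calculation depends only on response probabilities and patient counts. For example, 0.95^13 = 0.513, the stated 51.3%. Neither dosing rule enters it.

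**The case against.** **On creatinine.** A reader might infer that these patients have no way to continue, or that they lose treatment for good after one cycle. The text does not support that. Section 3.3.2 holds the drug and does not end treatment at once, so dosing can resume if creatinine falls to 1.5x ULN or below. The 21-day limit that takes a patient off treatment is stated only for holds beyond Cycle 2. What stands is narrower: while creatinine remains at its eligible entry value, no clause allows dosing to continue. The discretion in section 3.7 for patients with clinical benefit sits under restaging and does not waive the organ-function limits.

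**On hyperglycaemia.** A reader might infer that every asymptomatic Grade 3 value has two incompatible instructions. That is too broad, as the limits in the working show. There is also good evidence that Table 5 is meant to govern. It is a dedicated table, Table 4's non-haematological row expressly leaves hyperglycaemia out, and 3.3.2 points to Tables 4 and 5 for dose adjustments. An investigator would ordinarily follow the specific table. This reduces the weight of the point but does not remove it: no sentence gives Table 5 precedence, and the DLT-like definition has no hyperglycaemia exception.

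**On frequency.** Neither case has an expected count. Both hyperglycaemia DLTs described in section 1.2 were on other schedules, none occurred on 5/2, and section 11.1.12 reports none in the solid-tumour study. The phase 1 DLT definition is not given, so this does not exclude asymptomatic Grade 3 events, but it gives no reason to expect many.

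**Conclusion.** The creatinine rule is wrong as written. A patient enrolled on clearance whose creatinine does not change must be held from Cycle 2 at the latest and will have had at most 900 of 1,800 mg (50%) by first restaging, or none if 3.6.1 is read to cover Cycle 1. This assumes that the patient starts at full dose and that creatinine stays above 1.5x ULN.

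The hyperglycaemia wording is a lesser conflict, confined to a first asymptomatic Grade 3 episode that counts as an adverse event and improves within a week. Its size is 900 mg against 720 mg or 0 mg in the next cycle. Table 5 is the more specific rule and probably the intended one.

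Both groups are probably small, and the documents allow no estimate of either. A reader might go on to infer that the trial's efficacy conclusions are compromised. They are not on this ground: no sample size or efficacy error rate changes. The matter is consistent dosing of eligible patients, and it should be corrected because the correction is nearly free.

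**What to change.** Three one-line changes in one amendment:

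- **Sections 3.3.1 and 3.6.1**, creatinine item: add *or creatinine clearance at least 60 ml/min for patients enrolled by that route*. The per-minute unit is assumed, since 2.1.1.7 prints none; add it there as well.
- **Section 3.3.2**, after the sentence on dosing following a DLT-like event: add *For hyperglycemia, dosing follows Table 5*. Leave the DLT-like definition as it stands, so that the section 8 toxicity stopping rule is not altered as a side effect. Table 5's own reduction after a week without improvement stays in force.

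The cost is the amendment itself. Creatinine is already measured every cycle (section 3.4), and no patients, visits or procedures are added. The clearance floor of 60 ml still protects patients whose renal function worsens.

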3.4 EVALUATION DURING TREATMENT

Laboratory evaluations and physical examinations will be performed within two weeks prior to initial treatment and every three weeks (one cycle) while subjects are on therapy.

- CBC with differential and platelets
- Chemistries: Sodium (Na), Potassium (K), Chloride (Cl), Total CO₂ (bicarbonate), Creatinine, Glucose, Urea nitrogen (BUN), Albumin, Calcium total, Alkaline Phosphatase, ALT/GPT, AST/GOT, Total Bilirubin, Total Protein, cortisol, PT/PTT, TSH and thyroglobulin.
- Urinalysis

Within three days prior to each treatment cycle.

- Toxicity evaluation
- Vital signs, ECOG status, 12 L ECG

Abbreviated Title: CUDC-907 for thyroid cancer
Version Date: 10/11/2017

- Limited Physical examination

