Thrombocytopenia	2 (5%)	7 (16%)	2 (5%)	0
Neutropenia	2 (5%)	2 (5%)	2 (5%)	0
Upper respiratory infection	5 (11%)	1 (2%)	0	0
Constipation	5 (11%)	0	0	0
Cough	5 (11%)	0	0	0
Rash	5 (11%)	0	0	0
Hyperglycemia	0	1 (2%)	2 (5%)	0
Hypokalemia	2 (5%)	1 (2%)	0	0
Hypomagnesemia	2 (5%)	1 (2%)	0	0
Increased blood alkaline phosphatase	2 (5%)	1 (2%)	0	0
Dehydration	1 (2%)	1 (2%)	0	0
Dizziness	1 (2%)	1 (2%)	0	0
Epistaxis	1 (2%)	1 (2%)	0	0
Musculoskeletal pain	1 (2%)	1 (2%)	0	0
Pleural effusion	0	2 (5%)	0	0
Pneumonia	0	2 (5%)	0	0
Hypercalcaemia	0	0	1 (2%)	0
Lymphoma	0	0	0	1 (2%)
Sepsis	0	0	0	1 (2%)
Acute renal failure	0	1 (2%)	0	0
Anemia	0	1 (2%)	0	0
Cardiac tamponade	0	1 (2%)	0	0
Failure to thrive	0	1 (2%)	0	0
Hyperuricemia	0	1 (2%)	0	0
Influenza	0	1 (2%)	0	0

Lymph node pain	0	1 (2%)	0	0
Urosepsis	0	1 (2%)	0	0
Vascular access complications	0	1 (2%)	0	0

^Data from reference 22.

There was no DLTs observed in patients on the 5/2 schedule. Grade 3 or worse adverse events occurred in 19 (43%) of 44 patients. The most common of which were thrombocytopenia (9 of 44 patients [20%]), neutropenia (3 [7%]), and hyperglycemia (3 [7%]). Five (14%) of 37 response-evaluable patients achieved an objective response (two complete responses and three partial responses). All five responses occurred in the subgroup of patients with diffuse large B-cell lymphoma (DLBCL; n=9), and three occurred in those with transformed follicular lymphoma DLBCL (n=5). On the basis of these findings, we selected CUDC-907 60 mg on the 5/2 dosing schedule as the recommended phase 2 dose. As of 29 September 2015, CUDC-907 60 mg 5/2 had been administered to 15 subjects with solid tumors. Among 9 response-evaluable subjects as of data cut-off, there were 5 SDs (3 breast cancer, 1 adenoid cystic, 1 ovarian cancer) and 4 PDs (3 breast cancer, 1 salivary gland cancer). Based on this clinical experience, we will use 60 mg of CUDC-907 with the 5/2 schedule.

Plasma pharmacokinetics of CUDC-907 and the major metabolites were recently reported [22]. A dose-related increase in plasma exposure were observed. In six patients on the 60 mg 5/2 schedule, a low parent drug and metabolite concentrations in 0-24 hours were observed (24-hour plasma average concentration of active M2 metabolite and inactive M1 metabolite being 25 ng/mL and 20 ng/ml, respectively) [22].

Rationale for clinical protocol

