2.2.3 Within 2 weeks prior to treatment

- Laboratory Evaluations:
 - CBC with differential and platelets
 - Chemistries: Sodium (Na), Potassium (K), Chloride (Cl), Total CO₂ (bicarbonate), Creatinine, Glucose, Urea nitrogen (BUN), Albumin, Calcium total, Alkaline Phosphatase, ALT/GPT, AST/GOT, Total Bilirubin, Total Protein, cortisol, PT/PTT, TSH and thyroglobulin.
 - Urinalysis
- Complete history and physical examination including vital signs, height, weight and ECOG status
- 12 lead ECG

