3.5 STUDY CALENDAR

Procedures	Baseline Screening ⁶	Every Cycle (within 3 days)	Every 2 Cycles (within 3 days)	Off Treatment Evaluations (Following Treatment) ⁵				
				1 Month	3 Months	6 Months	12 Months	FU
Confirmation of thyroid cancer	X							
Informed Consent	X							
History and PE including height and weight	X							
Limited PE		X		X	X	X	X	
Vital signs	X	X						
Performance Score ECOG	X	X		X	X	X	X	
Toxicity evaluation	—————→							
12L ECG	X	X				X		
RECIST 1.1 disease assessment	X		X					
Urinalysis	X	X						
CBC with diff and platelets	X	X		X	X	X	X	
Chemistries ¹	X	X		X	X	X	X	
TSH and Thyroglobulin	X	X						
Serum or urine beta-HCG	X							
CT CAP or MRI	X		X	X	X	X	X	
Brain MRI or CT Scan	X							
Bone Scan	X							

Procedures	Baseline Screenin g ⁶	Every Cycle (within 3 days)	Every 2 Cycles (within 3 days)	Off Treatment Evaluations (Following Treatment) ⁵				
				1 Mont h	3 Mont hs	6 Mont hs	12 Mon ths	FU
Tumor Biopsy	X							
FDG PET Scan ²	X		X					
Phone/Email Evaluation ³								X
Advance Directives ⁴	X							

¹ Sodium (Na), Potassium (K), Chloride (Cl), Total CO2 (bicarbonate), Creatinine, Glucose, Urea nitrogen (BUN), Albumin, Calcium total, Alkaline Phosphatase, ALT/GPT, AST/GOT, Total Bilirubin, Total Protein, cortisol, PT/PTT

² 18F FDG PET scan will be performed after 2 cycles of treatment (+/- 3 days), and then annually or when clinical indicated.

³ Following the 12-month evaluation patients will be followed via phone or e-mail contact every 6 months for survival

⁴ Filling out of the advance directives will be offered, but obtaining of it is not required. For details see Section **10.3**

⁵ For follow up visits +/- window applies: +/- 1 week for 1 Month, +/- 2 weeks for 3 Month, +/- 4 weeks for 6 and 12 Months.

⁶ Evaluations done at screening will be used as Baseline assessments.

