3.8 OFF TREATMENT EVALUATIONS (FOLLOWING TREATMENT)

3.8.1 3 months

- Physical exam including ECOG status
- CBC with differential
- Chemistries: Sodium (Na), Potassium (K), Chloride (Cl), Total CO₂ (bicarbonate), Creatinine, Glucose, Urea nitrogen (BUN), Albumin, Calcium total, Alkaline Phosphatase, ALT/GPT, AST/GOT, Total Bilirubin, Total Protein
- CT scan of the chest, abdomen and pelvis (CT C/A/P) or MRI

3.8.2 6 months

- Physical exam including ECOG status
- CBC with differential
- Chemistries: Sodium (Na), Potassium (K), Chloride (Cl), Total CO₂ (bicarbonate), Creatinine, Glucose, Urea nitrogen (BUN), Albumin, Calcium total, Alkaline Phosphatase, ALT/GPT, AST/GOT, Total Bilirubin, Total Protein
- 12L ECG
- CT scan of the chest, abdomen and pelvis (CT C/A/P) or MRI

3.8.3 12 months

- Physical exam including ECOG status
- CBC with differential
- Chemistries: Sodium (Na), Potassium (K), Chloride (Cl), Total CO2 (bicarbonate), Creatinine, Glucose, Urea nitrogen (BUN), Albumin, Calcium total, Alkaline Phosphatase, ALT/GPT, AST/GOT, Total Bilirubin, Total Protein
- CT scan of the chest, abdomen and pelvis (CT C/A/P) or MRI

3.8.4 Following the 12-month evaluation patients will be followed via phone or e-mail contact every 6 months for survival

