4 SUPPORTIVE CARE

Appropriate supportive care for any side effects or toxicity may be provided by the Endocrine Oncology Branch. Patients may be admitted as necessary to manage issues related to study medication or disease process. Antidiarrheal treatment (e.g., loperamide) will be administered immediately upon the first onset of symptoms. Each subject will be instructed to have loperamide or a comparable anti-diarrheal medication readily available and to begin treatment for diarrhea at the first episode of poorly formed or loose stools or the earliest onset of bowel movements more frequent than normally expected for the subject until diarrhea free. Subjects will be instructed to notify the Investigator if diarrhea occurs and will be evaluated in the clinic for significant dehydration, possible electrolyte imbalance, and/or ongoing losses. If clinically significant dehydration is present, rehydration and electrolyte repletion will be performed. Additionally, subjects will be monitored following rehydration for the risk of recurrence and electrolyte imbalances and advised regarding appropriate fluid management to reduce the likelihood of subsequent dehydration events. Antiemetics will be given prophylactically after the first episode of nausea or vomiting. Growth factor support will be permitted for neutropenia or neutropenic fever.

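### Hypomagnesemia is a listed phase I toxicity, but no scheduled chemistry panel measures magnesium, so asymptomatic cases could be missed and the reported rate biased downward

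*Combined protocol and SAP*

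**What the plan says.** Section 1.2, Table 2, lists "Hypomagnesemia" among the toxicities of the phase I trial: 2 patients at Grade 1–2 and 1 at Grade 3, out of 44.

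The protocol itemises its chemistry tests in five places:

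- Screening (section 2.2.3): sodium through creatinine, glucose and urea, then "Calcium total, Alkaline Phosphatase, ALT/GPT, AST/GOT, Total Bilirubin, Total Protein, cortisol, PT/PTT, TSH and thyroglobulin".
- Every cycle on treatment (section 3.4): the same list, ending "Urea nitrogen (BUN), Albumin, Calcium total, Alkaline Phosphatase, ALT/GPT, AST/GOT, Total Bilirubin, Total Protein, cortisol, PT/PTT, TSH and thyroglobulin".
- Study calendar (section 3.5, footnote 1): the same list, ending "Calcium total, Alkaline Phosphatase, ALT/GPT, AST/GOT, Total Bilirubin, Total Protein, cortisol, PT/PTT"; TSH and thyroglobulin have their own row.
- 3, 6 and 12 months off treatment (section 3.8): a shorter list, ending "Calcium total, Alkaline Phosphatase, ALT/GPT, AST/GOT, Total Bilirubin, Total Protein".
- The safety visit about 30 days after the last dose (section 3.9): the same shorter list.

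Sodium, potassium, chloride, bicarbonate and total calcium are in all five. Magnesium is in none. Its only other appearance in the protocol is as part of an excipient in the capsule.

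Three sets of rules bear on the omission. Section 3.3.2 makes a "Non-hematological \geq Grade 3 AE" a DLT-like event, with one exception for nausea and vomiting. Table 4 ties management of Grade 3 non-hematological events to recovery to Grade 1 or baseline, and calendar footnote 6 makes the screening evaluations the baseline. Section 4 says that a patient with diarrhea "will be evaluated in the clinic for significant dehydration, possible electrolyte imbalance, and/or ongoing losses", without naming analytes.

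**The concern.** Low magnesium is a laboratory finding and may cause no symptoms. A site that follows the calendar exactly obtains no magnesium value before treatment and none routinely during it. The protocol's own evidence names the toxicity, at the same frequency and grade split as hypokalemia (2 at Grade 1–2 and 1 at Grade 3), and potassium is measured at every cycle. The documents give no reason for treating the two differently.

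Two things are at stake. First, this is a single-arm trial, so its safety table is only as complete as the tests scheduled. A low count of hypomagnesemia would be read as evidence about the drug when it may partly reflect not having looked. Second, the Grade 3 and return-to-baseline rules presuppose a value. Even a case found by unscheduled testing would have no pre-treatment result to compare with.

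**Working it through.** **Inputs.** Phase I counts: 2 at Grade 1–2, 1 at Grade 3, 0 at Grades 4 and 5, denominator 44 (section 1.2 and Table 2). Planned size: 40 evaluable patients, accrual ceiling 50 (section 8). Toxicity rule: stop enrolling if the cumulative fraction with DLTs reaches 1/3 once 6 or more patients have been accrued (section 8).

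**Step 1: reproduce the plan's figures.** 2/44 = 4.5%, printed as 5%; 1/44 = 2.3%, printed as 2%. Both agree. Any grade: (2 + 1)/44 = 3/44 = 6.8%.

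**Step 2: check the panels.** Magnesium appears in 0 of the 5 chemistry lists. The lists are intact and consistent with one another, so broken text or redaction does not explain the gap.

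**Step 3: expected cases if the phase I rate p carries over.** Expected cases = n × p; chance of at least one = 1 − (1 − p)^n; ranges use exact (Clopper-Pearson) 95% limits for p.

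| Event | p (95% limits) | Expected in 40 | Expected in 50 | At least one in 40 | At least one in 50 |
|---|---|---|---|---|---|
| Any grade | 6.8% (1.4% to 18.7%) | 2.7 (0.6 to 7.5) | 3.4 (0.7 to 9.3) | 94% | 97% |
| Grade 3 | 2.3% (0.06% to 12.0%) | 0.9 (0.02 to 4.8) | 1.1 (0.03 to 6.0) | 60% | 68% |

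**Step 4: how many of these could reach the database.** Section 6.2.3 keeps Grade 1 events out of C3D, and Table 2 does not split Grades 1 and 2. If both lower-grade phase I cases were Grade 1, only the Grade 3 rate matters (0.9 in 40). If both were Grade 2, all three count (2.7 in 40). The recordable number at the point estimate therefore lies between 0.9 and 2.7.

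**Step 5: direction of the bias.** Let d be the share of recordable cases found by unscheduled testing. The expected recorded number in 40 is then between 0.9 × d and 2.7 × d. The documents give no value for d. Any d below 1 biases the reported rate downward, by a factor of d.

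**Step 6: bearing on the stopping rule.** With 40 patients, 40/3 = 13.3, so the threshold is 14 patients with DLTs. About one expected Grade 3 case in the whole trial is small against 14. A single case could plausibly matter only very early, when the threshold is 2 of 6.

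**The case against.** A reader might infer that every case would go undetected and that the schedule finds none. The documents do not support this. Section 3.4 requires a toxicity evaluation and an ECG each cycle. Section 4 sends patients with diarrhea for an electrolyte evaluation, and section 11.1.12 puts diarrhea at 63% on this dose and schedule, so that trigger will be common. Section 7.1.1 makes a laboratory abnormality an adverse event if it is symptomatic, treated or judged of significant clinical impact. Nothing forbids a clinically indicated test. What remains is that none of these routes names magnesium, and all depend on symptoms or a clinician's choice.

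A reader might also infer that the stopping rule is compromised. That does not follow. Section 8 counts DLTs, section 3.3.2 defines DLT-like events, and no text equates the two. Even if they are the same, about one expected event is unlikely to decide a one-third threshold. The any-grade figures should not be used to size this harm, which concerns Grade 3 only.

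The evidence is also thin. The 44 patients had lymphoma or myeloma, only seven were on the 5/2 schedule, and Table 2 does not say on which schedule the three cases arose. Section 11.1.12 does not name hypomagnesemia among the most common events of either study. This limits the size of the point but does not explain the omission.

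Comparing it with hyperglycemia (also 3 of 44) would overstate the case: all three of those events were Grade 3 or 4. An argument from QTcF also fails. The 480 msec limit is a screening exclusion, and the documents give no on-treatment QTc rule linked to magnesium.

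Finally, no passage promises to assay every event in Table 2, so this is a gap in ascertainment and not a contradiction. That is fair.

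**Conclusion.** The point holds as a gap in safety ascertainment. Magnesium is in none of the scheduled panels although the protocol's own table lists hypomagnesemia, including a Grade 3 case. Asymptomatic cases could be missed unless tested outside the schedule, the reported rate would be biased downward by an amount the documents do not let one estimate, and the Grade 3 and return-to-baseline rules have no scheduled magnesium value to act on.

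The size is modest: about 2.7 any-grade and 0.9 Grade 3 cases expected in 40 patients, with the wide limits shown in the table. These figures assume that rates from a hematologic population pooled over schedules carry over to thyroid cancer patients on 60 mg 5/2. The omission alone is unlikely to change the stopping decision, and it affects no sample size, error rate or efficacy conclusion. The omission itself is certain; how many cases it would hide is not. The change is worth making because it is specific and cheap.

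**What to change.** Add magnesium to the chemistry list at screening (section 2.2.3), at each cycle (section 3.4 and calendar footnote 1) and at the 30-day safety visit (section 3.9). Footnote 1 serves the whole chemistries row of the calendar, so it should say that magnesium applies to the baseline, each-cycle and 1-month columns. If the sponsor prefers not to add the test, the protocol should state why magnesium is left out despite Table 2.

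The 3-, 6- and 12-month panels do not need it: beyond 30 days after treatment, section 6.2.2 captures only serious, unexpected and related events. Uric acid does not need adding on this evidence either; Table 2 shows one case of hyperuricemia in 44.

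The cost is one extra assay per listed time point, on blood already drawn, and a wording change in four places. No visit, procedure, dose rule or design figure changes.
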